### 6.3.6 Bladder Diary

Patients/parents/caregivers will collect bladder diary data [REDACTED]

[REDACTED]. For screening, the bladder diary can be completed [REDACTED] [REDACTED]. The same person(s) (patient or parent(s)/caregiver) should complete the bladder diary throughout the study where possible. For example, if the patient is able to complete the bladder diary themselves during the screening period, they should complete it themselves throughout the study. If a parent or caregiver will assist or complete on the patient's behalf, then this should be done throughout the study.

The bladder diary will capture the following information:

- day/date, time, and type (urinary incontinence, catheterization, voluntary void) of each voiding episode during the daytime (time between waking up to start the day and going to bed to sleep for the night)
- volume of urine on catheterization at morning wakening
- time of night sleep and morning wakening
- whether urinary incontinence occurred during the night

More detailed instructions on the patient bladder diary will be provided to the patient and parent/caregiver.

The diary data will be used to satisfy eligibility requirements for study entry, as well as for qualification for retreatment.

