### 7.2.1 Primary Efficacy Variable

The primary efficacy variable is the change from baseline posttreatment in the daily average frequency of daytime urinary incontinence episodes (daytime is defined as the time between waking up to start the day and going to bed to sleep for the night). The daily average frequency of daytime urinary incontinence episodes is obtained using the total number of daytime urinary incontinence episodes recorded in a 2-day bladder diary divided by 2, and baseline frequency is defined as the daily average frequency of episodes of daytime urinary incontinence preceding the study treatment. Each daytime period recorded in the bladder diary is normalized to represent a 12-hour period to account for differing durations of the daytime period. The daily average frequency of daytime urinary incontinence episodes will be adjusted by the normalized daytime period.

The primary timepoint will be week 6 posttreatment.

For the baseline and posttreatment data, a patient must have at least 1 valid diary day (defined as a day where there is 1 or more urinary episodes [eg, incontinence, catheterization, or voluntary void] during the daytime collection period [between waking to start the day and going to bed to sleep at night]). In the case of patients who partially complete their diary, providing that at least 1 valid diary day out of 2 is available, the 2-day frequency of daytime urinary incontinence will be prorated with the value from the valid diary day.

If less than 1 diary day out of 2 has been completed, then the frequency of daytime urinary incontinence will be considered as missing. Missing frequency of episodes of daytime urinary incontinence at baseline will be imputed using the median of all nonmissing values at baseline within the same treatment group. For the scheduled visits up to week 6 after the study treatment, missing frequencies of episodes of daytime urinary incontinence will be replaced using the last observation carried forward approach. No imputation will be done for missing values on visits after the week 6 visit.

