2.3.1 Diary Data Conventions

- For baseline and post-treatment visits, analyses will be based on the diary data collected over two consecutive days. “Wake time information” will be collected for each diary day including the time the patient woke up in the morning and presence/absence of night time leaking by accident (from the previous night), as well as the time and volume of urine collected on the first morning catheterization. “Day time information” will be collected for each diary day including date, time, and type of voiding episode [leak by accident (i.e. urinary incontinence), urinated with catheter, urinated without catheter (i.e. voluntary void)] for each daytime episode (from time after waking up to start the day and doing the first morning catheterization, and going to bed to sleep for the night). Lastly, “bed time information” will be collected for each diary day including the time the patient went to bed for the night.
- Note: Recording day time urinary events should begin *after* the 1st morning catheterization (as the urine expelled is from the previous night). In cases where the patient erroneously re-entered the first morning catheterization event as a day time event (ie, the time of 1st morning catheterization and the time of the first day time urinary event are the same), the event will not be included in the analysis for day time events.
- The visit windows [REDACTED] will be used to derive a patient’s diary parameters for each visit.
 - A valid diary day is defined as a day where there are one or more urinary episodes of any type (incontinence, catheterization, or voluntary void) during the daytime

collection period. In the case of patients who provide just one valid diary day within a visit window, the 2-day frequency of daytime urinary incontinence will be prorated with the value from the valid diary day.

- If there are no valid diary days within the window, the 2-day diary data will be set as missing for the visit.
- For baseline and post-treatment visits, the 2-day diary will be determined based on the following algorithm:
 - 1) Apply visit windows [REDACTED] which are based on days from the date of study drug injection.

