- The daily frequency of daytime urinary incontinence episodes will be normalized to a 12-hour daytime period. The following normalization algorithm will be used:
 - 1) Apply visit window [REDACTED] which uses days from treatment as reference.
 - 2) Identify wake time and bedtime within the visit window. Daytime period (in hours) is determined by time between wake time and bedtime for that day.
 - 3) Using the example below, 4 urinary incontinence episodes are recorded during the first daytime period of 16 hours (7:00am to 11:00pm), and 7 episodes recorded during the second daytime period of 14 hours (8:30am to 10:30pm).

April 3	April 4

Wake time 7:00am Bed time 11:00pm (16 hrs)
 
4 urinary incontinence episodes during the daytime collection period (beginning after the 1st morning catheterization and until bed time)
	
Wake time 8:30am Bed time 10:30pm (14 hrs)
 
7 urinary incontinence episodes during the daytime collection period (beginning after the 1st morning catheterization and until bed time)

On a given day, the number of daytime urinary incontinence episodes normalized to a 12-hour daytime period will be calculated by

$$\frac{12}{\text{daytime period}} \times \text{number of daytime urinary incontinence episodes} ,$$

which, in the example, adjusts to 3 ($= (12/16) \times 4$) and 6 ($= (12/14) \times 7$) normalized urinary incontinence episodes, respectively. The daily average frequency of daytime urinary incontinence episodes by the normalized daytime period in a given visit window will be 4.5 ($= (3 + 6)/2$) in this example.

- If wake time is missing, the missing wake time will be imputed by the first morning catheterization where urine volume is collected. If both the wake time and the first morning catheterization are missing then the morning wake time will be imputed by either the first urinary episode time of any type recorded on that day or 7:00 am, whichever comes earlier. If bedtime is missing, the missing time will be imputed by either the last urinary episode time of any type recorded on that day or 10:00 pm, whichever comes later.

3. Disposition and Exit Status

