4.5 Past Medical History

Medical history information will be coded with the MedDRA dictionary. Frequencies and percentages will be summarized by MedDRA primary System Organ Class (SOC) and preferred term for the mITT population.

5. Efficacy Analyses

Efficacy analyses will be performed on the mITT population. The primary time point for efficacy will be week 6. Efficacy data will also be presented by study visit using the visit windows [REDACTED].

5.1 Collection of Primary Efficacy Measurement(s) and Derivation of Primary Efficacy Variable(s)

The primary efficacy variable is the change from baseline to post-treatment in the normalized daily average frequency of daytime urinary incontinence episodes (daytime is defined as the time between waking up to start the day and 1st morning catheterization, and going to bed to sleep for the night). The daily average frequency of daytime urinary incontinence episodes is obtained using the total number of daytime urinary incontinence episodes recorded in a 2-day bladder diary divided by 2, and baseline frequency is defined as the daily average frequency of episodes of daytime urinary incontinence preceding the study treatment (ie, obtained from the screening diary).

Each daytime period recorded in the bladder diary is normalized to represent a 12-hour period to account for differing durations of the daytime period between and within different patients (see Section 2.3 for further details). Furthermore, if there is just 1-day of valid bladder diary data, this will be used as the daily average frequency of daytime urinary incontinence episodes (see Section 2.3 for further details).

The primary time point for this change from baseline endpoint will be week 6 posttreatment.

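### The SAP counts daytime leaks from the first morning catheterization but divides by hours from waking; the protocol starts daytime at waking, and the departure is not declared.

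*SAP*

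**What the plan says.** **Protocol.** Section 7.2.1 defines the primary variable with the words "daytime is defined as the time between waking up to start the day and going to bed to sleep for the night". Section 6.3.6 gives the diary the same daytime. Section 7.2.1 also normalizes each recorded daytime period to 12 hours.

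**SAP, what is counted.** Section 2.3.1 says recording of daytime events should begin after "the 1st morning catheterization (as the urine expelled is from the previous night"). Its normalization example counts "episodes during the daytime collection period (beginning after the 1st morning catheterization and until bed time").

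**SAP, what it is divided by.** The same section states: "Daytime period (in hours) is determined by time between wake time and bedtime for that day". Its example uses 16 and 14 hours, both measured from wake time. The May example, also in 2.3.1, starts the period used for normalization at the 7:30 am wake time, although catheterization is at 7:33 am.

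**SAP, primary variable.** Section 5.1 says "daytime is defined as the time between waking up to start the day and 1st morning catheterization"; the sentence then runs on to bedtime. It names both waking and catheterization at the start of the day and does not say which governs.

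**Related rules in SAP 2.3.1.** A missing wake time is replaced by the first morning catheterization time. An event is left out when a patient re-entered the first morning catheterization as a daytime event, identified as the case where "the time of 1st morning catheterization and the time of the first day time urinary event are the same".

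**Deviations.** SAP section 12 declares none.

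**The concern.** This is the derivation of the primary endpoint, and three things do not fit together.

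- **Counting window.** A leak after waking and before catheterization is a daytime episode under the protocol and is outside the SAP's window. The SAP's reason, that the urine comes from the night before, explains leaving out the catheterized urine. It does not say where a leak in that gap belongs. The night-time item is a yes/no question about the previous night, so it would not replace a counted episode.
- **Rate.** Episodes from one interval are divided by the length of a longer one. When wake time is missing the two intervals coincide, so identical days can receive different rates depending on whether wake time was recorded.
- **Duplicate rule.** Its test is equal times and does not mention event type.

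Two programmers could derive different primary values from this text. The responder categories in SAP 5.3 include a 100% reduction, so a patient whose only remaining leak fell in the gap could be classed as fully dry.

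**Working it through.** **1. The plan's own figure.** SAP formula: (12 / daytime hours) × episodes, averaged over two days.

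(12/16) × 4 = 3; (12/14) × 7 = 6; (3 + 6)/2 = 4.5. This matches the SAP. The arithmetic is right; the question is the definition.

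**2. Denominator only.** Let T be wake-to-bed hours and g the gap from waking to catheterization. With the SAP's count n, the SAP rate is 12n/T and the matched rate is 12n/(T − g). The SAP rate is therefore too low by the fraction g/T.

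| Case | g | T | g/T |
|---|---|---|---|
| SAP May example, day 1 (7:30 to 7:33 am) | 3 min | 15.5 h | 0.05/15.5 = 0.3% |
| SAP May example, day 2 (12:00 to 12:10 pm) | 10 min | 13 h | 0.167/13 = 1.3% |
| Assumed | 30 min | 14 h | 0.5/14 = 3.6% |
| Assumed | 60 min | 14 h | 1/14 = 7.1% |

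The May example has one leak on each day. The SAP mean is (12/15.5 + 12/13)/2 = 0.849. Starting the divisor at catheterization gives (12/15.45 + 12/12.833)/2 = 0.856, a rise of 0.9%.

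For scale, Protocol 7.7 cites an adult mean change of −3.1 episodes/day. With the same gap at baseline and week 6, 1.3% of 3.1 is 0.04.

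**3. Numerator.** One uncounted leak on one of the two days lowers that patient's average by 0.5 × 12/T:

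- T = 15.5 h: 0.5 × 12/15.5 = 0.39
- T = 13 h: 0.5 × 12/13 = 0.46

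With one such leak on both days of the 16 h and 14 h example, the average would be (12/16 × 5 + 12/14 × 8)/2 = 5.304 instead of 4.5, a difference of 0.80.

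These are effects on one visit's value. If waking leaks are as frequent at week 6 as at baseline, and the daytime lengths are the same, they cancel in the change. If they fall, the reduction is understated; if they rise, it is overstated.

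**4. Dose comparison.** Only a difference between groups in the change in waking leaks moves the treatment contrast. Assume the net share of patients who lose one waking leak per day differs between two groups by 10% to 30%. The difference in means then shifts by 0.10 × 0.80 = 0.08 to 0.30 × 0.80 = 0.24 episodes/day, in either direction. The planning half-widths in Protocol 7.7 are reproduced by 1.96 × SD × √(2/30): 1.012 at SD 2.0 and 2.024 at SD 4.0. The shift is thus between 0.08/2.024 = 4% and 0.24/1.012 = 24% of a half-width. The imbalance is purely an assumption.

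**5. Duplicate rule.** The May example shows a leak and a catheterization both at 2:46 pm. That pair is not at the first catheterization and nothing removes it. It shows only that the diary can hold two event types at the same minute.

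**The case against.** The strongest reply is that the gap is short by design. Protocol 6.3.6 places the first catheterization at morning wakening, and the SAP's own gaps are 3 and 10 minutes. The 30 and 60 minute gaps appear nowhere in the documents. Protocol 7.5 also plans the analysis without normalization, which removes the divisor, and SAP 5.2.1 summarizes daytime duration by visit. This stands for the denominator. It does not reach the numerator, because dropping the normalization leaves the counting start where it is.

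A reader might infer that the SAP deletes genuine leaks. The documents do not show this. The duplicate rule is aimed at re-entered catheterizations, which never enter the incontinence count, and no rule explicitly removes a leak entered in the gap at another time. What stands is narrower: such a leak lies outside the stated counting period, and the equal-times test, read literally, could remove a leak logged at the same minute as the first catheterization.

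A reader might also infer that the reduction from baseline is attenuated. That would require waking leaks to be common and to fall with treatment, and the documents report neither. The same rule applies at every visit and in every group.

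Nor was the rule concealed: the SAP's Amendment 3 summary records the recording note and explains it. It is missing from section 12, where departures from the protocol belong.

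Finally, leaks before catheterization may have no timed entry. SAP 2.3.1 describes daytime collection as starting after catheterization, and the diary form is not in the documents. This stands, and it makes the fix conditional.

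**Conclusion.** The mismatch is in the current text: the protocol starts daytime at waking, the SAP counts from the first catheterization, it divides by hours from waking, and it declares no departure. The denominator part is minor, 0.3% and 1.3% on the SAP's example days; 3.6% to 7.1% holds only for assumed gaps of 30 to 60 minutes in a 14 h day. The numerator part can matter more for an individual patient, at 0.39 to 0.46 episodes/day for each uncounted leak on one of two days. Its effect on the dose comparison has unknown size and direction, because the frequency of waking leaks is not given and only a difference between groups would bias the contrast. The point should be corrected because it decides how the primary endpoint is computed, not because a bias has been demonstrated.

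**What to change.** Use one start point for numerator and denominator, and state it identically in SAP 2.3.1 and 5.1.

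- If leaks between waking and the first catheterization have timed diary entries, count them from wake time over wake-to-bed hours, as Protocol 7.2.1 defines.
- If they were not collected, start the denominator at the first morning catheterization as well, and list the change from Protocol 7.2.1 in SAP section 12.
- In either case, restrict the duplicate rule to catheter events recorded at the time of the first morning catheterization, so that a leak is never removed.

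Under the first option the replacement of a missing wake time by catheterization time remains an approximation and should be described as one.

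The cost is SAP wording and derivation code. Which option applies can be settled by checking the diary form and the recorded entries before database lock.

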3.1 Screening Log Data

A listing of patients that screen failed will be generated for patients that signed informed consent. The listing will include information on demographic characteristic (sex, race and age) and reason for screen failure.

3.2 Disposition and Exit Status

The patient disposition table for this study will be based on the mITT population. A listing of patients' disposition information will also be generated. This patient listing will also include information on the study duration.

3.3 Study Duration

In this study patients only get one injection of study drug hence, the duration of exposure to study treatment and study duration will be the same. For details on how to analyze duration of exposure to study treatment see [REDACTED]

3.4 Protocol Deviations

Significant and non-significant deviations are defined in the Protocol Deviations Specification Document and will be determined prior to database lock. A by patient protocol deviation listing will be produced for the significant protocol deviations. The deviation type and detail will be presented.

4. Demographics and Other Baseline Characteristics

Demographic and baseline characteristics will be analyzed using the mITT population. Baseline assessments are defined to be assessments taken prior to study drug injection.

4.1 Demographics

Age, race, sex, weight (kg) and height (cm) will be summarized by treatment group and overall. Race will be summarized as Caucasian, Black, Asian, Hispanic, and Other.

4.2 Disease Characteristics

The following baseline information will be summarized using the mITT population:

- baseline information on stratification factors (age < 12 vs \geq 12 years; daytime urinary incontinence \leq 6 vs. $>$ 6 episodes),
- baseline bladder characteristics (presence or absence of open bladder neck, external sphincter dyssynergia, fecal incontinence, bladder sensation with filling, and whether or not the patient is ambulatory),
- baseline bladder wall thickness

- use of anticholinergic therapy at baseline (on day of injection),
- number of prior anticholinergic therapy used for urinary incontinence
- duration of prior anticholinergic therapy used for urinary incontinence
- reason prior anticholinergic therapy not considered to adequately managed urinary incontinence
- daily average frequency of normalized daytime urinary incontinence episodes,
- daily average urine volume at first morning catheterization (mL),
- presence/absence of night time urinary incontinence,
- number of urinary tract infection (UTI) within 6 months prior to screening
- A patient's neurological characteristics, and
- urodynamic assessments namely, presence or absence of involuntary detrusor contraction (IDC), maximum cystometric capacity (MCC) (mL), maximum detrusor pressure during the first IDC ($P_{detMax1stIDC}$) (cm H₂O) if IDC present, maximum detrusor pressure (P_{detMax}) (cm H₂O) during the storage phase, and detrusor leak point pressure (DLPP) (cm H₂O).

4.3 Prior Medications

Prior medications are defined as any medications which are administered prior to the BOTOX injection. The mITT population will be used for the analysis of prior medications.

4.3.1 Prior Anticholinergic Medications for Urinary Incontinence

The frequency and percentage of prior anticholinergic medications for urinary incontinence will be summarized by WHO Drug Class and WHO DDE preferred drug name. A summary of the primary reason for not being adequately managed by prior anticholinergic medication will also be presented.

4.3.2 Antibiotic Medication for Prophylactic Treatment

All prophylactic antibiotic medication associated with study drug treatment will be summarized by WHO Drug Class and WHO DDE preferred drug name. Such medications will not be classified as either prior or concomitant medication.

4.4 Concomitant Medications/Procedures

A concomitant medication is any medication which is administered any time after the study drug injection, irrespective of when the medication started or stopped.

4.4.1 Concomitant Anticholinergic Medications for Urinary Incontinence

Concomitant anticholinergic medication for urinary incontinence will be summarized by WHO Drug Class and WHO DDE preferred drug name as described for the prior medication using the mITT population.

4.4.2 Concomitant Medication

Concomitant medications will be summarized by WHO Drug Class and WHO DDE preferred drug name as described for the prior medication using the mITT population.

4.4.3 Concurrent Procedures

A patient listing of concurrent procedures will be produced using the mITT population.

4.5 Past Medical History

Medical history information will be coded with the MedDRA dictionary. Frequencies and percentages will be summarized by MedDRA primary System Organ Class (SOC) and preferred term for the mITT population.

5. Efficacy Analyses

Efficacy analyses will be performed on the mITT population. The primary time point for efficacy will be week 6. Efficacy data will also be presented by study visit using the visit windows [REDACTED].

5.1 Collection of Primary Efficacy Measurement(s) and Derivation of Primary Efficacy Variable(s)

The primary efficacy variable is the change from baseline to post-treatment in the normalized daily average frequency of daytime urinary incontinence episodes (daytime is defined as the time between waking up to start the day and 1st morning catheterization, and going to bed to sleep for the night). The daily average frequency of daytime urinary incontinence episodes is obtained using the total number of daytime urinary incontinence episodes recorded in a 2-day bladder diary divided by 2, and baseline frequency is defined as the daily average frequency of episodes of daytime urinary incontinence preceding the study treatment (ie, obtained from the screening diary).

Each daytime period recorded in the bladder diary is normalized to represent a 12-hour period to account for differing durations of the daytime period between and within different patients (see Section 2.3 for further details). Furthermore, if there is just 1-day of valid bladder diary data, this will be used as the daily average frequency of daytime urinary incontinence episodes (see Section 2.3 for further details).

The primary time point for this change from baseline endpoint will be week 6 posttreatment.

